7.5 Preparation/Handling/Storage/Accountability

The investigational product should be stored in a secure area according to local regulations. It is the responsibility of the investigator to ensure that investigational product is only dispensed to study Participants. The investigational product must be dispensed only from official study sites by authorized personnel according to local regulations.

The product storage manager should ensure that the study treatment is stored in accordance with the environmental conditions (temperature, light, and humidity) as determined by BMS. If concerns regarding the quality or appearance of the study treatment arise, the study treatment should not be dispensed and contact BMS immediately.

Study treatment not supplied by BMS will be stored in accordance with the package insert.

Investigational product documentation (whether supplied by BMS or not) must be maintained that includes all processes required to ensure drug is accurately administered. This includes documentation of drug storage, administration and, as applicable, storage temperatures, reconstitution, and use of required processes (e.g., required diluents, administration sets).

Further guidance and information for final disposition of unused study treatment are provided in [Appendix 2](#) and pharmacy manual.

7.5.1 Dosing of Cabiralizumab and Nivolumab

For patients in the monotherapy cohorts, cabiralizumab infusion will be administered as a 30-minute IV infusion on Day 1 of each 14-day treatment cycle. For the combination therapy, nivolumab should always be administered first as a 30-minute IV infusion followed by a 30-minute infusion of cabiralizumab. The time in between infusions is expected to be approximately 30 minutes but may be more or less depending on the situation. Cabiralizumab ± Nivolumab will be administered every 2 weeks in 14-day (\pm 2 days). Subjects may be dosed no less than 12 days from the previous dose.

Dosing calculations should be based on the body weight assessed at Cycle 1 Day 1 prior to the first dose of study drug administration. If the subject's weight on the day of dosing differs by $> 10\%$ from the weight used to calculate the prior dose, the dose must be recalculated. All doses should be rounded to the nearest milligram.

The calculated dose for Cabiralizumab may be mixed in 5% Dextrose Injection, USP or 0.9% Sodium Chloride Injection, USP to nominal concentrations of 1.0 mg/mL to 10 mg/mL which can be infused over a period of 30 minutes through an intravenous line containing a sterile 0.22 micron in-line filter. Further guidance and information for the preparation of the study medication is provided in the pharmacy manual.

The calculated dose for Nivolumab may be mixed in 5% Dextrose Injection, USP or 0.9% Sodium Chloride Injection, USP to nominal concentrations of 1 mg/mL – 10 mg/mL which can be infused over a period of 30 minutes through an intravenous line containing a sterile, non-pyrogenic, low-protein binding in-line filter. Further guidance and information for the preparation of the study medication is provided in the pharmacy manual.

[figure not shown]
Doses of study drugs may be interrupted, delayed, or discontinued depending on how the patient tolerates the treatment.

[figure not shown]
[figure not shown]
[figure not shown]
7.5.2 *Retained Samples for Bioavailability / Bioequivalence*

Not Applicable.

7.6 *Treatment Compliance*

Study treatment compliance will be periodically monitored by drug accountability. Drug accountability should be reviewed by the site study staff at each visit to confirm treatment compliance. Sites should discuss discrepancies with the participant at each on-treatment study visit.

7.8 Treatment After the End of the Study

At the end of the study, BMS will not continue to provide BMS supplied study treatment to participants/investigators unless BMS chooses to extend the study. The investigator should ensure that the participant receives appropriate standard of care to treat the condition under study.

8 DISCONTINUATION CRITERIA

8.1 Discontinuation from Study Treatment

Participants MUST discontinue investigational product (and non-investigational product at the discretion of the investigator) for any of the following reasons:

- Participant's request to stop study treatment. Participants who request to discontinue study treatment will remain in the study and must continue to be followed for protocol specified follow-up procedures. The only exception to this is when a participant specifically withdraws consent for any further contact with him/her or persons previously authorized by participant to provide this information
- Any clinical AE, laboratory abnormality or intercurrent illness which, in the opinion of the investigator, indicates that continued participation in the study is not in the best interest of the participant
- Termination of the study by Bristol-Myers Squibb (BMS)
- Loss of ability to freely provide consent through imprisonment or involuntarily incarceration for treatment of either a psychiatric or physical (e.g., infectious disease) illness
- Documented disease progression or clinical deterioration while receiving active study therapy with exception as described in [section 7.4.4](#).
- Pregnancy
- Patients who are required to have prohibited concomitant medications
- Inability to comply with protocol

Refer to the Schedule of Activities for data to be collected at the time of treatment discontinuation and follow-up and for any further evaluations that can be completed

All participants who discontinue study treatment should comply with protocol specified follow-up procedures as outlined in [Section 2](#). The only exception to this requirement is when a participant withdraws consent for all study procedures including post-treatment study follow-up or loses the ability to consent freely (i.e., is imprisoned or involuntarily incarcerated for the treatment of either a psychiatric or physical illness).

If study treatment is discontinued prior to the participant's completion of the study, the reason for the discontinuation must be documented in the participant's medical records and entered on the appropriate case report form (CRF) page.

8.1.1 Dose Discontinuation Criteria for Cabiralizumab and Nivolumab

Discontinuation rules may be different for monotherapy and combination therapy and not all rules will apply to both arms of the study. For comprehensive discontinuation rules, refer to [Appendix 6](#) (monotherapy) and [Appendix 7](#) (combination therapy) or [Appendix 8](#) (laboratory abnormalities).

Treatment of cabiralizumab in monotherapy or cabiralizumab in combination with nivolumab should be discontinued in the following cases unless otherwise specified:

- Any Grade 3 or higher uveitis *or* any Grade 2 drug-related uveitis, eye pain, or blurred vision that does not respond to topical therapy and does not improve to Grade 1 within the second re-treatment period *or* that requires systemic treatment

- Any Grade 3 or higher infusion-related reactions and hypersensitivity requiring discontinuation. Any re-initiation of therapy in this circumstance would require consultation with the Sponsor's Medical Monitor or designee.
- Any Grade 3 non-skin, drug-related AE lasting >7 days, including drug-related uveitis, pneumonitis, hypoxia, bronchospasm, and endocrinopathies with the following exceptions:
 - Grade 3 drug-related endocrinopathies adequately controlled with only physiologic hormone replacement do not require discontinuation
 - Grade 3 drug-related laboratory abnormalities do not require treatment discontinuation except:
 - Grade 3 drug-related thrombocytopenia >7 days or associated with Grade ≥ 2 bleeding requires discontinuation
- Any drug-related liver function test (LFT) abnormality that meets any one of the following criteria requires discontinuation:
 - ALT or AST $>3x$ ULN **and** total bilirubin $>2x$ ULN **or** INR $>1.5 \times$ ULN (in the absence of anticoagulation).
 - See [Appendix 6](#) and [Appendix 7](#) for guidelines and possibility of restarting therapy
 - ALT or AST $>20x$ ULN (with or without concurrent liver metastases)
 - Total bilirubin $>3x$ ULN ($>5x$ ULN with concurrent liver metastases)
- Any Grade 4 drug-related AE or laboratory abnormality, except for the following events which do not require discontinuation:
 - Grade 4 neutropenia <7 days
 - Grade 4 lymphopenia or leukopenia <7 days
 - Isolated Grade 4 amylase or lipase abnormalities that are not associated with symptoms or clinical manifestations of pancreatitis. The Sponsor's Medical Monitor or designee should be consulted for Grade 4 amylase or lipase abnormalities.
 - Isolated Grade 4 electrolyte imbalances/abnormalities that are not associated with clinical sequelae and are corrected with supplementation/appropriate management within 72 hours of their onset
 - Grade 4 drug-related endocrinopathy AEs, such as adrenal insufficiency, adrenocorticotropic hormone (ACTH) deficiency, hyper- or hypothyroidism, or glucose intolerance, which resolve or are adequately controlled with physiologic hormone replacement (corticosteroids, thyroid hormones) or glucose-controlling agents, respectively, may not require discontinuation after discussion with and approval from the Sponsor's Medical Monitor or designee.
 - Grade 4 CK up to $20 \times$ ULN (in the absence of clinical sequelae)
- Any event that leads to delay in dosing lasting >6 weeks from the previous dose requires discontinuation, with the following exceptions:
 - Dosing delays to manage drug-related adverse events are allowed. Prior to re-initiating treatment in a patient with a dosing delay lasting >6 weeks from the previous dose, the Sponsor's Medical Monitor or designee must be consulted. Tumor assessments should continue as per-protocol even if dosing is delayed. Periodic study visits to assess safety and laboratory studies should also continue per protocol, or more frequently if clinically indicated during such dosing delays or per the Investigator's discretion.
 - Dosing delays lasting >6 weeks from the previous dose that occur for non-drug-related reasons may be allowed if approved by the Sponsor's Medical Monitor or designee.

Prior to re-initiating treatment in a patient with a dosing delay lasting >6 weeks, the Sponsor's Medical Monitor must be consulted. Tumor assessments should continue per protocol every 8 weeks (± 7 days) even if dosing is delayed. Periodic study visits to assess safety and laboratory studies should also continue per-protocol or more frequently if clinically indicated during such dosing delays or per the Investigator's discretion.

- Any AE, laboratory abnormality, or intercurrent illness which, in the opinion of the Investigator, presents a substantial clinical risk to the patient with continued cabiralizumab and/or nivolumab dosing
- Any Grade 3 or higher neurological toxicity
- Any Grade 3 or higher periorbital edema and persistent Grade 2 periorbital edema requiring 2 missed doses unless approved by Sponsor's Medical Monitor
- Any Grade 3 or higher drug-related diarrhea or colitis, which does not resolve to Grade 1 or baseline within 28 days.
- Any Grade 4 skin toxicity
- Any Grade 4 renal toxicity
- Any Grade 3 or higher pulmonary toxicity
- If the causality of the adverse event requiring discontinuation is confirmed to be due to one of the study drugs in the combination therapy, the other drug may be continued per protocol schedule under the following scenarios:
 - Timely resolution of the adverse event based on the treatment modification table
 - Clinical benefit is shown by the patient based on Investigator assessment

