7.4.2 Criteria to Resume Treatment with Cabiralizumab and Nivolumab

Patients may resume treatment with cabiralizumab and/or nivolumab when the drug-related AE resolves as noted in the AE management tables in Appendix 6 and Appendix 7 or the abnormal laboratory management table in Appendix 8. The Sponsor's Medical Monitor or designee can be contacted at any time if further clarification is needed.

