^b If the AE requiring discontinuation was due to one of the study drugs, the non-offending drug may be continued, if there is timely resolution of AE and clinical benefit is shown by patient

^c Patients on IV steroids may be switched to an equivalent dose of oral corticosteroids (e.g. prednisone) at start of tapering or earlier, once sustained clinical improvement is observed. Lower bioavailability of oral corticosteroids should be taken into account when switching to the equivalent dose of oral corticosteroids.

Uveitis Adverse Event Management		
Grade of Uveitis (NCI CTCAE v4.03)	Management	Follow-Up
Grade 1	
 – Observe symptoms – Continue cabiralizumab and nivolumab therapy 	
 – Watch for worsening of symptoms including visual disturbances, light sensitivity, decrease vision – Monitor weekly 
If worsens:
 
 – Follow as stated below
Grade 2	
 – Delay or discontinue cabiralizumab and nivolumab therapy per protocol^{a,b} – Start antibiotics and inflammatory medications including steroids^c – Ophthalmologic consult, if clinically indicated – Immunosuppressive agents (e.g. anti-TNF agents such as Infliximab) 	
If symptoms resolve within 14 days:
 
 – Continue cabiralizumab and nivolumab therapy at same dose level and start tapering of steroid doses 
If symptoms resolve between 14 - 28 days:
 
 – Consider continuing dosing at same dose level for nivolumab and a dose level lower for cabiralizumab on resolution to baseline or Grade 1 and start tapering of steroid doses. – If it is Grade 2 drug related uveitis which does not resolve within 14 days, consider to discontinue study drug(s) 
If symptoms persist or worsen in 28 days regardless of systemic treatment:
 
 – Discontinue both cabiralizumab and nivolumab therapy – Continue monitoring of symptoms including visual disturbances, eye pain, and dimness of vision and follow up until resolution or return to baseline – Continue steroids, antibiotics, and other medications such as infliximab, as clinically indicated

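### Appendix 7 offers a cabiralizumab dose reduction for Grade 2 uveitis that 7.4.3 forbids and is not aligned with the 8.1.1 uveitis stop; separately, the INR limit in the liver stopping rule differs between 8.1.1 and all four hepatic tables (minor)

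*Protocol*

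**What the plan says.** **Uveitis.** Protocol 8.1.1 lists Grade 2 drug-related uveitis as a reason to stop in two alternative forms. One is "any Grade 2 drug-related uveitis, eye pain, or blurred vision that does not respond to topical therapy and does not improve to Grade 1" (with a time limit tied to re-treatment). The other is an event "that requires systemic treatment". Appendix 7, which covers the combination cohorts, handles Grade 2 uveitis in a table row. Its action is "Delay or discontinue cabiralizumab and nivolumab therapy per protocol", its listed treatment includes steroids and "Immunosuppressive agents (e.g. anti-TNF agents such as Infliximab", and its follow-up has these branches:

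- Resolution within 14 days: "Continue cabiralizumab and nivolumab therapy at same dose level and start tapering of steroid doses".
- Resolution between 14 and 28 days: consider nivolumab at the same dose and cabiralizumab one level down. If the uveitis is drug-related and unresolved at 14 days, stopping is only to be considered.
- Persistence or worsening at 28 days: stop both drugs.

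Protocol 7.4.3 and SAP 7.4.3 both rule out dose reduction for either drug, without conditions. Appendix 6 (monotherapy) has no uveitis table.

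**INR.** In 8.1.1, AST or ALT above 3 x ULN combined with bilirubin above 2 x ULN or INR above 1.5 x ULN requires stopping. The INR arm applies only to patients not on anticoagulants, and the potential-DILI definition in 9.2.7 uses the same limit. The matching row in all four hepatic tables (Appendices 6 and 7, with and without liver metastasis) prints INR above 1.5, with no ULN multiple and no anticoagulation exemption.

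**Order of authority.** Section 8.1.1 says "For comprehensive discontinuation rules, refer to" the appendices, and its list applies to treatment that "should be discontinued in the following cases unless otherwise specified". Section 7.4.2 adds: "Patients may resume treatment with cabiralizumab and/or nivolumab when the drug-related AE resolves as noted in the AE management tables". No sentence says which text wins if they differ.

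**The concern.** These rules decide whether a patient with eye or liver toxicity is dosed again. A site that follows the Appendix 7 uveitis row may give a reduced cabiralizumab dose that the protocol bars, or may re-dose a patient whom 8.1.1 would take off treatment. A site that works from 8.1.1 alone may miss a stop that the hepatic table requires.

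There is a smaller consequence for the analysis. SAP 7.1.1 identifies AEs leading to discontinuation from the action recorded on the CRF, so the rule a site picks feeds that count. The INR point can reach the primary safety endpoint (monotherapy). The uveitis point reaches only the secondary combination safety endpoint. The analysis is descriptive, so the patient-level decision is the main issue.

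**Working it through.** The plan gives no figure to reproduce. The check is a comparison of text plus a little arithmetic.

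**Step 1: uveitis, case by case (combination cohorts, Grade 2, drug-related).**

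- *Needs systemic treatment, resolves within 14 days.* 8.1.1: stop. Appendix 7: continue both drugs at the same dose with a taper. The texts differ if the row's treatment is systemic.
- *Needs systemic treatment, resolves between 14 and 28 days.* 8.1.1: stop. Appendix 7: consider stopping, or consider continuing with less cabiralizumab. They differ on the same condition, and the reduction also breaks 7.4.3.
- *Topical treatment only, resolves between 14 and 28 days.* The systemic-treatment clause in 8.1.1 is not met. Appendix 7 still offers the reduction, and 7.4.3 still forbids it.
- *Persists or worsens at 28 days on systemic treatment.* Both texts stop.

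The dose-reduction conflict therefore does not depend on how the treatment is classified, whereas the stopping mismatch does. Three things favour the systemic reading: the footnote attached to the steroids concerns intravenous and oral steroids, infliximab is listed, and the 28-day branch presupposes systemic treatment. The row never says so for the earlier branches.

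**Step 2: can the lower dose be rescued?** The combination dose in Table 7.1-1 is 4 mg/kg and the next listed level is 2 mg/kg, so one level down is 2/4 = 50% of the dose. Section 7.1 allows a lower dose only where a dose level is found to exceed the MTD, after consultation. That is not one patient's uveitis. The proviso in 8.1.1 qualifies the 8.1.1 list, not 7.4.3. The branch limits are 14/14 = 1 and 28/14 = 2 dosing cycles.

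**Step 3: INR gap.** The documents give no local ULN for INR, so these values are assumed. Gap = 1.5 x ULN - 1.5, in patients not anticoagulated:

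| Assumed ULN | 8.1.1 limit | Table limit | Gap |
|---|---|---|---|
| 1.0 | 1.50 | 1.50 | 0 |
| 1.1 | 1.65 | 1.50 | 0.15 |
| 1.2 | 1.80 | 1.50 | 0.30 |

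For any ULN of 1.0 or more, 1.5 x ULN is at least 1.5. Every patient who meets the INR arm of 8.1.1 then also meets the table row. The table is the wider, stricter rule and the other is nested inside it. In an anticoagulated patient with INR above 1.5 and AST or ALT above 3 x ULN, the two INR arms differ whatever the ULN.

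The INR arm can decide the action. With AST or ALT above 5 and up to 12 x ULN and bilirubin at or below 2 x ULN, the tables continue dosing if there are no clinical signs of significant muscle or liver damage. An INR of 1.6 at an assumed ULN of 1.1 moves that patient into the table's stopping row but does not meet the 8.1.1 rule. Section 6.1 sets the entry limit at 1.5 x ULN in every cohort. At that ULN a subject could enter with INR 1.65, already above the table's 1.5.

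**Step 4: ceilings.** Combination: 12 + 12 = 24 subjects (5.1.2). All cohorts: 12 + 24 = 36, taking the upper end of the 6 to 12 expected in monotherapy. These are planned maxima, not affected counts.

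**The case against.** **The appendices govern.** Section 8.1.1 calls them comprehensive and carries a proviso, and 7.4.1 and 7.4.2 send delays, modifications and resumption to the tables. This points towards the appendices but does not settle it. The disputed uveitis and hepatic rows are themselves qualified by *per protocol*, which points back to the body. It also does nothing for the dose reduction, which 7.4.3 bars outright.

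**The uveitis row can be read consistently.** *Delay or discontinue per protocol* can mean: stop if systemic treatment is needed, otherwise delay and use the branches. This reading is available, and the row does not label its treatment systemic. A reader might infer that the row plainly orders re-dosing of patients on systemic therapy. The text does not go that far, though that is its natural sense, and 7.4.2 prevents confining the branches to events unrelated to study drug.

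**The INR rules do not contradict each other.** This stands. Section 8.1.1 never requires continuation below its limit, so at a ULN of 1.0 or more a site that follows the table breaks nothing in 8.1.1. The failure runs one way only. The tables also allow restart in selected circumstances, such as another cause being found, once the sponsor or Medical Monitor and the investigator agree.

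**There is a safety net.** Section 9 requires immediate safety concerns to be discussed with the sponsor to decide whether the participant continues, and the hepatic rows call for Medical Monitor contact. This limits the harm considerably. It does not say which printed rule applies, and the Grade 2 uveitis row asks for no such contact.

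**Conclusion.** The point holds as a minor drafting inconsistency with three parts of unequal strength:

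- The lower-dose option in the Appendix 7 uveitis row contradicts 7.4.3 and SAP 7.4.3, with no inference needed.
- The row's continue branches are out of line with the systemic-treatment stop in 8.1.1, if the listed steroids and infliximab are systemic.
- The INR limit is printed in two forms. The difference matters for anticoagulated patients and for laboratories with a ULN above 1.0. The default under the tables is the safer rule.

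The INR gap of 0 to 0.30 rests on assumed ULNs of 1.0 to 1.2. The documents give no event rates, so 24 and 36 are enrolment ceilings and no expected count is stated.

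Two stronger readings are not supported. A reader might infer a third conflict over Grade 3 diarrhea, because 8.1.1 stops for Grade 3 non-skin events lasting more than 7 days while Appendix 7 allows 28 days. But 8.1.1 has its own diarrhea and colitis bullet with the same 28-day limit, so any tension lies between two bullets inside 8.1.1. A reader might also infer an effect on DLTs or dose escalation; none is shown here.

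**What to change.** 1. In the Appendix 7 Grade 2 uveitis row, delete the option of a lower cabiralizumab dose.
2. State in that row that Grade 2 drug-related uveitis needing systemic treatment is discontinued under 8.1.1, so that the 14-day and 28-day continue branches apply only otherwise.
3. Print one bracketed expression in 8.1.1 and all four hepatic tables: AST or ALT >3 x ULN AND (total bilirubin >2 x ULN OR the INR limit). The sponsor's safety physicians should choose between INR >1.5 x ULN with the anticoagulation exemption and the stricter absolute INR >1.5.
4. Add one sentence to 8.1.1 saying which text governs when it and an appendix differ.

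The cost is wording in one protocol amendment and a site notice. No extra patients, visits or tests are needed.

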8.1.2 Post Study Treatment Study Follow-up

In this study, safety and tolerability information is a key endpoint of the study. Post study follow-up is of critical importance and is essential to preserving participant safety and the integrity of the study. Participants who discontinue study treatment must continue to be followed for collection of outcome for at least 100 days after the last dose of study therapy.

